## **7.8. Patient Voiding Diary**

The Patient Voiding Diary is used by participants (via the eDiary or paper Diary) to record the frequency of daily OAB symptoms including all micturations, urgency, incontinence, and main reason for incontinence by selecting the respective box for each symptom occurring during the course of a given day and night.

The Patient Voiding Diary should be completed by the patient on all of the 7 days prior to the Weeks 16, 24, 44, and 52 Visits.

A “**Diary Day**” is defined as the time between when the patient gets up for the day each morning (i.e., the time the patient got up for the day yesterday to the time the patient got up for the day today; approximately a 24-hour period).

A “**Complete Diary Day**” is defined as a Diary Day for which the patient indicates that they have recorded all urinations and any leakages that occurred during that Diary Day. More specifically, a “Complete Diary Day” is defined as a Diary Day that includes input of micturition data by patients on the voiding diary, and unless a patient indicated “No” to the questions of “Did you record each time you urinated or leaked during this Diary Day”, the Diary Day is considered complete.

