#### **5.1.1. Inclusion Criteria**

1. Has completed participation in study RVT-901-3003.
2. Willing and able to provide written informed consent.
3. For females of reproductive potential: Agrees to remain abstinent or use (or have their male partner use) an acceptable method of birth control (as defined in Section 5.2.1) each time the patient has intercourse until the Follow-up Visit.
4. For females of reproductive potential: Agrees not to donate ova (eggs) until at least 1 month after the last dose of Study Treatment.
5. Has demonstrated  $\geq 80\%$  compliance with self-administration of Study Treatment in study RVT-901-3003.
6. Has completed a minimum of 4 Complete Diary Days for study RVT-901-3003 Week 12.
7. Is ambulatory and in good general physical and mental health as determined by the Investigator.
8. In the opinion of the Investigator, is able and willing to comply with the requirements of the protocol, including completing questionnaires, the Voiding Diary, and Voided Volume Diary (will require ability to collect, measure, and record voided volume by herself/himself using a graduated urine collection and measurement container [provided by the Sponsor, if needed]).

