## **7.6. Inclusion/Exclusion Criteria**

Prior to randomization in RVT-901-3004, all inclusion and exclusion criteria will be reviewed by the Investigator or qualified designee to ensure that the patient qualifies for the study.

All inclusion criteria must be met and none of the exclusion criteria may apply. No eligibility waivers will be granted.

Patients found ineligible during review of inclusion/exclusion will not proceed through the randomization process.

Compliance with self-administration of Study Treatment in study RVT-901-3003 will be calculated based on the tablet/capsule counts recorded in the IxRS of the Run-In and Treatment phase in study RVT-901-3003 (Visits #2 through Visit # 6).

Laboratory results from the Week 4 Visit of RVT-901-3003 study will be used as a basis to confirm eligibility for glucose, AST, ALT, and eGFR. Urine pregnancy test, Urine dipstick results, ECG and average blood pressure measure will be confirmed prior to randomization. Concomitant medications will be reviewed at to ensure required stability.

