#### 9.3.1. Efficacy Endpoints

For the purpose of this study, the number of micturitions will be defined as the number of times a patient has voided in the toilet as indicated on the Voiding Diary. Average daily micturitions are calculated using the daily entries in the Voiding Diary, which is completed prior to each study visit. Average daily number of micturitions will be calculated as the total number of micturitions that occur on a Complete Diary Day divided by the number of Complete Diary Days in the Voiding Diary. A “Complete Diary Day” is defined as a Diary Day that includes input of micturition data by patients on the voiding diary. Unless a patient indicated “No” to the questions of “Did you record each time you urinated or leaked during this Diary Day”, the Diary Day is considered complete. Baseline is defined as the average number of micturitions occurring during the week of Run-in prior to the Baseline Visit in study RVT-901-3003. If data from the study RVT-901-3003 Run-in are not available for a patient, data collected during Screening will serve as the baseline.

[figure not shown]
The number of UUI episodes will be defined as the number of times a patient has checked "urge" as the reason for accidental urine leakage. Average daily urge urinary incontinence episodes at each study visit will be calculated in the same manner as described above for the micturition endpoint. The urge urinary incontinence endpoint will be analyzed using only OAB Wet patients.

[figure not shown]
Secondary Endpoints:

- Change from baseline (CFB) at Week 52 in average number of micturitions per 24 hours in all OAB patients
- CFB at Week 52 in average number of urge urinary incontinence (UUI) episodes per 24hours in OAB Wet patients

- CFB at Week 52 in average number of urgency episodes (need to urinate immediately) over 24 hours in all OAB patients
- CFB at Week 52 in average number of total urinary incontinence episodes over 24 hours in OAB Wet patients

Exploratory Endpoints:

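### Do the two wordings of Complete Diary Day in section 7.8 leave the diary endpoints or inclusion criterion 6 ill-defined?

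*Protocol*

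**What the plan says.** Section 7.8 describes a Complete Diary Day twice in a row. The first sentence makes it "a Diary Day for which the patient indicates that they have recorded all urinations and any leakages that occurred during that Diary Day". The second presents itself as the more specific version: a day with micturition input counts as complete "unless a patient indicated “No” to the questions of" whether each urination or leak was recorded.

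Section 9.3.1 drops the first sentence and keeps the second rule. There a Complete Diary Day "is defined as a Diary Day that includes input of micturition data by patients on the voiding diary", again with the proviso that only a No answer disqualifies it. The visit value is "the total number of micturitions that occur on a Complete Diary Day divided by the number of Complete Diary Days in the Voiding Diary", and urge incontinence episodes "will be calculated in the same manner as described above for the micturition endpoint". On the reference value it says: "Baseline is defined as the average number of micturitions occurring during the week of Run-in prior to the Baseline Visit in study RVT-901-3003".

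The term also sets an eligibility threshold. Inclusion criterion 6 (section 5.1.1 and the synopsis) reads "Has completed a minimum of 4 Complete Diary Days for study RVT-901-3003 Week 12", and section 7.6 adds "No eligibility waivers will be granted".

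**The concern.** Two consecutive sentences give different answers for the same kind of day. Under the first, silence on the completeness question means the day does not count; under the second, it does. If an unanswered day was only partly filled in, it adds a whole day to the denominator of the mean but only some of its events to the numerator, so the mean is too low.

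That could matter more here than in a comparative analysis. Section 9.5.1 reports each arm's own adjusted mean with its interval and no treatment difference, so an error common to both arms does not cancel. The threshold of four days in criterion 6 could also turn on which sentence is applied. The question can plausibly go unanswered: every patient is given a paper diary as back-up, and the protocol does not say that the eDiary forces an answer.

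**Working it through.** **Step 1: where the two wordings differ.** For a day with micturition input:

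| Answer to the completeness question | 7.8, first sentence | 7.8, second sentence, and 9.3.1 |
|---|---|---|
| Yes | complete | complete |
| No | not complete | not complete |
| none | not complete | complete |

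Only the last row differs. A partly recorded day answered Yes counts under both, so it is a separate matter. An unanswered but fully recorded day does no harm under the 9.3.1 rule.

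**Step 2: effect of one day on one visit mean.** The formula is that of 9.3.1: total on Complete Diary Days divided by their number. The seven-day diary comes from 7.8; 11 micturitions per day and half recorded are assumptions.

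- Counted: (6 × 11 + 5.5)/7 = 10.21, against 11.0 if fully recorded, a difference of -0.79.

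The choice between the wordings, however, is between counting the day and leaving it out, and there the direction is not fixed. Suppose the other six days average 10 and the affected day truly had 15:

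- 12 recorded: (60 + 12)/7 = 10.29 counted, 10.0 excluded, 75/7 = 10.71 fully recorded. Counting is nearer the truth.
- 7.5 recorded: (60 + 7.5)/7 = 9.64 counted, 10.0 excluded. Excluding is nearer.

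**Step 3: effect on change from baseline, relative to full recording.** Let B and P be the true daily counts at baseline and Week 52, qB and qP the shares of counted days that are both partial and unanswered, and r the share of events recorded on them. Then

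bias = (1 - r)(B·qB - P·qP).

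None of these inputs is in the protocol. With B = 11, P = 9 (true change -2.00) and r = 0.5:

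| Share of counted days | Week 52 only: -0.5 × 9 × q | Equal at both times: 0.5 × (11 - 9) × q | Baseline only: 0.5 × 11 × q |
|---|---|---|---|
| 1% | -0.045 | +0.01 | +0.055 |
| 2% | -0.09 | +0.02 | +0.11 |
| 5% | -0.225 | +0.05 | +0.275 |
| 1/7 | -0.643 | +0.143 | +0.786 |

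Varying r from 0.75 to 0.25 moves the Week 52-only figure at 2% from -0.045 to -0.135. With seven days each, a 1% share means 7% of patients have one such day (0.07/7 = 0.01). The 1/7 row needs every patient to have one, so it is an upper illustration. A Week 52-only shift of 0.1 per day needs a share of 0.1/(0.5 × 9) = 2.2%. For urge incontinence, assumed 3.5 falling to 1.5, 2% at Week 52 only gives -0.5 × 1.5 × 0.02 = -0.015.

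The sign turns when qP/qB passes B/P = 11/9 = 1.22. Nothing in the protocol says on which side of that ratio the trial lies.

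**Step 4: eligibility.** Seven days with input, three answered Yes and four unanswered, are 3 Complete Diary Days by the first sentence (criterion 6 fails) and 7 by the second (criterion met). This shows the wordings can diverge. But the days in criterion 6 are Week 12 diary days collected in RVT-901-3003, and how that study counted them is not shown here.

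**The case for a change.** The best argument for a change is that this is a contradiction in the protocol, not detail left to the SAP. A more specific sentence ought to narrow the general one; this one admits days the general one shuts out. The arm-level means have no comparator difference in which a shared error could cancel. Eligibility is decided before any SAP applies. Paper diaries make unanswered days possible, and repairing one clause costs almost nothing. A repeat of the four secondary models on days answered Yes would use data already collected.

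Much of this is correct. The wording conflict is real, the non-cancellation point is sound, and a tidy-up of 7.8 would do no harm. It falls short on consequence:

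- The programmer works from 9.3.1, which has one rule, and that rule says what happens to an unanswered day.
- The effect is nil if the eDiary forces an answer and paper goes unused.
- Several provisions work against partial days: morning confirmation of entries (7.8.1, 7.11.2), reminder calls on about days 1 and 3 (7.10), site and monitor review of diary entries (8.3), and mandatory discontinuation of patients who cannot complete the Voiding Diary (5.5). None proves the share is zero, but each lowers it.
- A repeat on Yes days has its own selection problem. It discards fully recorded days on which the question was skipped and leans towards diligent reporters.

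**Conclusion.** The concern identifies a true inconsistency of wording but not an error in the analysis. The first sentence of 7.8 is a loose general description left beside the working rule. The second sentence and 9.3.1 agree with each other and fix the treatment of an unanswered day, so an analyst would compute the endpoints in one way only. Treating silence as complete is also a fair trade-off: it keeps fully recorded days that a strict rule would lose, at the price of keeping some partial ones.

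On the assumed inputs, shares of 1% to 2% move the mean change in micturitions by less than 0.1 per day at half recording when they fall at Week 52 only, and by +0.01 to +0.02 when equal at both times. Larger shifts need larger shares or less complete recording, for which the protocol offers no evidence; smaller ones, including zero, are equally open. The affected output is descriptive, without p-values or treatment differences, and the primary endpoint is safety. Whether the Run-in baseline and the Week 12 eligibility count used the same day rule depends on RVT-901-3003 documents not at hand, and is a detail the study team can confirm without altering this plan.

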### **7.8.1. Patient Voiding Diary Training/Re-Training**

#### All Visits

The site staff should inquire whether patients had any difficulties with the diary and address any questions patients may have.

Instructions for proper completion of the Patient Voiding Diary should be re-reviewed, and, if available, patients may view an instructional video to reinforce their understanding of Patient Voiding Diary instructions.

Patients will be trained to enter data immediately following each event (in real time) and to input data from any “missed” events as soon as they are able. They will review and confirm that data from all events occurring within the preceding Diary Day (approximately 24 hours) have been entered at a consistent time each morning (e.g., upon getting up for the day).

## **7.9. Urine Volume Diary**

Urine volume data are collected separately by patients using the Urine Volume component of the eDiary, or the paper Urine Volume Chart. The Urine Volume Chart is a tool routinely used in clinical practice and clinical investigation to assess voiding functions over a 24-hour period and is regarded as a useful instrument in the investigation of patients with voiding symptoms. Urine volume may be collected during any one (1) of the 7 Diary Days prior to the visit, and it should be recorded for ~24-hours starting from the time the patient gets up for the day and continues until the time the patient gets up for the day on the next day.

Patients will be asked to complete the Urine Volume Diary to record their urine volume passed during that day. The Urine Volume collection and Urine Volume Diary completion should be performed by the patient on a day that they choose for one (1) complete day of the 7 days prior to the Weeks 16, 24, 44, and 52 Visits. The definition of a Diary Day and data entry instructions

will be the same as for the Patient Voiding Diary (i.e., the data should be recorded in real time, morning to morning).

### **7.9.1. Urine Volume Collection Training/Re-Training**

At each subsequent visit the site staff should confirm the patient's understanding and ability to measure a volume of water as practice.

Patients should be instructed that on the days the paper Urine Volume Chart Diary is completed:

- Every micturition recorded on the Patient Voiding Diary must have a corresponding entry recorded on the Urine Volume Chart (this is automatically done on the eDiary).
- Every entry recorded on the Urine Volume Chart must have a corresponding micturition recorded on the Patient Voiding Diary (this is automatically done on the eDiary).

Site staff should reinstruct the patient on Urine Volume collection procedures as needed. Instructions for proper completion of the Urine Volume Chart should be re-reviewed, and, if available, patients may view an instructional video to reinforce their understanding of the Urine Volume Chart and collection instructions.

### **7.9.2. Dispense Urine Collection and Measurement Supplies**

The urine collection and measurement container (if needed) are reusable and should be rinsed by patients and reused for the days that they will be collecting their urine volume throughout the study. Patients should be reminded to keep the urine collection container with them during the period of time when urine volume is being collected.

### **7.10. Reminders for Diary Collection**

The site will phone the patient on approximately the first day and the third (or next business days) of the 7 Diary collection days. Patients will be reminded to enter data immediately following each micturition (in real time); they will also be asked to input data from any "missed" events and confirm that data from all micturitions occurring within the preceding 24 hours have been entered at a consistent time each morning (e.g., upon getting up for the day). Patients may consent to receive additional reminders via SMS text to their personal mobile phone. In addition to visit reminders, these diary completion reminders will be sent the day before each diary collection period begins (to remind patients to start diary completion) and two days prior to the end of each diary collect window (to ensure urine volume collection has been completed prior to the visit).

### **7.11. Electronic Diary**

The Electronic Diary (eDiary) for this study includes both the Patient Voiding Diary and the Urine Volume Diary and will be implemented via an eDiary device (provisioned smartphone). Paper diaries will be provided to all patients to be used when necessary. When a paper diary is used, it should be collected at each visit.

### **7.11.1. eDiary Device Set-Up and Training**

#### Device Setup/Function Check

The eDiary device will be set-up by the site at the Week 12 Visit and dispensed to the Patient. At each subsequent visit, site personnel will check that the device is functioning correctly. Instructions on how to perform the set-up task will be provided by the Sponsor.

### **7.11.2. Device Training/Re-Training**

The site staff should inquire whether patients had any difficulties with the diary and address any questions patients may have.

Instructions for proper completion of the eDiary should be re-reviewed, and, if available, patients may be asked to view an instructional video to reinforce their understanding of Patient Voiding Diary instructions.

Patients will be asked to enter data immediately following each micturition (in real time); they will also be asked to input data from any “missed” micturition and confirm that data from all micturitions occurring within the preceding 24 hours have been entered at a consistent time each morning (e.g., upon getting up for the day).

## **7.12. Patient-Reported Outcomes**

Patients will complete paper questionnaires at the site at the start of each required study visit to assess patient-perceived symptom relief, symptom bother, and health-related quality of life at the study visits. These include the following questionnaires:

- Global Impression Items include Patient Global Impression of Severity (PGI-Severity), Patient Global Impression of Control (PGI-Control), Patient Global Impression of Frequency (PGI-Frequency), Patient Global Impression of Leakage (PGI-Leakage), and Patient Global Impression of Change (PGI-Change).
- Overactive Bladder Questionnaire (OAB-q long form [OAB-q LF], 1-week recall) is a multi-item questionnaire that was developed to assess symptom bother and the impact of overactive bladder on health-related quality of life. The instrument was developed and validated in both continent and incontinent OAB patients, including both men and women.
- Work Productivity and Activity Impairment Questionnaire-Urinary Symptoms (WPAI-US), version 2.0, is a 6-item questionnaire that assesses health-related work productivity loss due to urinary symptoms with a 1-week recall period.
- The EQ-5D health questionnaire is a standardized instrument for use as a measure of health outcome [Rabin, 2014]. It is applicable to a wide range of health conditions and treatments; it provides a simple descriptive profile and a single index value for health status.

The Investigator should not provide any additional information to patients prior to completing the questionnaires which might influence responses.

### **7.13. Post-Void Residual Volume**

The risk of acute urinary retention or morbidities related to an increase in Post-Void Residual (PVR) is a concern with antimuscarinic therapy that promotes smooth muscle relaxation by inhibiting acetylcholine-induced smooth muscle contraction. If, during contraction, the bladder cannot generate enough pressure to overcome the outlet resistance in the urethra, either because of poor detrusor contractility or profound obstruction (most commonly from BPH), acute urinary retention or incomplete emptying of the bladder may result.

The volume of urine that remains in the bladder after voiding (PVR) is an objective measurement that may serve as a proxy for impaired ability to void. The physician should assess patients with an increase in PVR for an adverse event.

PVR will be performed via ultrasound at the visits indicated in the Schedule of Activities in Section 1.1. All efforts will be made to ensure the same device and operator are used for all PVR measurements for individual patients.

### **7.14. Physical Examination**

Focused physical examinations will include examination of heart, lungs, abdomen as well as any other organ system in which a previous abnormality was noted at Baseline (in study RVT-901-3003) or relates to a patient complaint of an adverse event.

### **7.15. Electrocardiogram**

A single twelve-lead ECG will be performed at the Week 12 Visit and may be performed, as clinically indicated, at an Unscheduled Visit.

All ECGs should be performed after 10 minutes of rest in a semi-recumbent position.

### **7.16. Vital Signs**

Vital signs including blood pressure, heart rate, respiration rate, and temperature (oral or tympanic) will be obtained at all visits after patients have rested quietly in a sitting position for 5 minutes.

Three blood pressure measurements will be taken in a sitting position and performed on the same arm and by the same site staff, if possible, for each patient throughout the study. The following instructions should be followed:

- Sitting systolic and diastolic blood pressures will be determined by averaging 3 replicate measurements obtained 1 to 2 minutes apart. The average of the 3 replicate blood pressure measurements will be used for eligibility and safety assessments (not an individual value).

The same method for assessing temperature should be used at all visits for a particular patient.

Body weight will be measured with patients in street clothing with jacket/coat and shoes removed.

## **7.17. Adverse Events**

Spontaneously reported adverse events will be recorded at each visit. The Investigator or site staff is responsible for detecting, documenting, and reporting events that meet the definition of an adverse event or serious adverse event. See Section 8 for details on adverse event definitions and reporting.

## **7.18. Clinical Laboratory Assessments**

Details regarding specific laboratory procedures/assessments to be performed in this study are provided below. The total amount of blood/tissue to be drawn/collected over the course of the study (from pre-study to post-study visits), including approximate blood/tissue volumes drawn/collected by visit and by sample type per patient can be found in [Appendix 3](#).

Please refer to the Schedule of Activities (Section 1.1) for specific laboratory tests performed at each study visit.

